4.2.1 Primary Outcome Variables/Endpoints

The following are the primary outcome variables and associated measures that will be administered at all three time points (i.e., baseline, 3-months post-baseline, and 6-months post-baseline) in the study:

- LGBTQ Clinical Skills Competency
 - Sexual Orientation Counselor Competency Scale (SOCCS) – Clinical Skills subscale – 11-items from a psychometrically validated measure, based on a 7-point Likert scale assessing the extent to which respondents endorse clinical competence as related to their skills in working with clients of diverse sexual identities. For the present study, items have been adapted to specifically assess competence in clinical skills based on an LGBTQ-affirmative CBT framework.
 - Deliberate Practice of LGBTQ-Affirmative CBT Skills: 2 brief video clips (less than 1 minute each) of fictional clients will be presented. Participants will be asked to write a brief paragraph describing what clinical approaches they would use in their clinical treatment in order to address the challenges

discussed by the fictional client. These written responses will be used to assess participants' LGBTQ-affirmative CBT skills.

- Cultural Humility
 - Multidimensional Cultural Humility Scale (MCHS) – a 15-item self-report psychometrically validated measure assessing the extent to which respondents endorse an ability to maintain an other-oriented, interpersonal stance in relation to cultural identities most salient to clients. For the present study, items were adapted to specifically assess cultural humility as related to working with LGBTQ clients.
- Content Knowledge, Familiarity, and Use of Minority Stress & CBT
 - Minority Stress Content Knowledge Quiz – 10 multiple choice items developed by the researchers for the purpose of this study to assess respondents' content knowledge of minority stress
 - CBT/LGBTQ-Affirmative CBT Content Knowledge Quiz – 10 multiple choice items developed by the researchers for the purpose of this study to assess respondents' content knowledge of CBT/LGBTQ-affirmative CBT
 - Familiarity and Use of LGBTQ-Affirmative CBT Skills Questionnaire – 14 items rated on a 5-point Likert scale that was developed by the researchers for the purposes of this study assessing respondents' familiarity with and use of LGBTQ-affirmative CBT skills

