NCT04559698

Title of Research Project: Assessing mental health providers' clinical knowledge and skills via an online training on LGBTQ-affirmative cognitive-behavioral therapy

Date: 12.7.21

Assessing Mental Health Providers Clinical Knowledge and Skills Via an Online Training on LGBTQ-affirmative Cognitive-behavioral Therapy

Statistical Analysis Plan

Feasibility and Acceptability

Feasibility was assessed in terms of training attendance. Acceptability was assessed in terms of a 7-item measure we created for the present study presented to participants immediately following the intervention (immediate $n = 52$, waitlist control $n = 44$). Sum scores were taken for each participant, and means and standard deviations were recorded for each condition to determine training acceptability.

Intervention Efficacy

Intervention efficacy was assessed using an intent-to-treat analysis and included all participants ($n = 121$). First, to test the effectiveness of randomization, we examined differences in baseline participant demographic and professional characteristics between the immediate intervention condition ($n = 61$) and waitlist control ($n = 60$) using t -tests for continuous measures and chi-square tests for categorical measures. Age, fulltime employment status, and number of years working in LGBTQ mental healthcare differed between conditions ($p < .10$), with the waitlist control group containing participants with a younger mean age, who were less likely to be working fulltime, and who reported fewer years working in LGBTQ mental healthcare. Thus, we included fulltime employment status and number of years working in LGBTQ mental health care as covariates in subsequent analyses. We did not include age as a covariate because of its high correlation ($r = .50$) with number of years working in LGBTQ mental healthcare. Dependent variables were assessed for normality using skewness thresholds of ± 2 and kurtosis

thresholds of ± 7 (Byrne, 2010; Hair et al., 2010), and all dependent variables were considered normal except simulated practice skills for general CBT. To meet model assumptions of normal distribution, scores on the simulated practice skills for general CBT scale were square-root transformed prior to efficacy analyses.

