To examine intervention efficacy, we used linear mixed models with maximum likelihood estimation and an unstructured covariance matrix to test the Condition \times Time interaction for all intervention outcomes including LGBTQ cultural competence, LGBTQ cultural humility, minority stress knowledge, LGBTQ-affirmative CBT knowledge, LGBTQ-affirmative CBT skills familiarity, LGBTQ-affirmative CBT skills use, LGBTQ-affirmative simulated practice skills, and general CBT simulated practice skills. Primary analyses between conditions were limited to baseline (time = 0) and 4-months post-baseline assessment (time = 1; changed from 3-months post-baseline prior to the beginning of the study) and examined the Condition \times Time effect of receiving immediate intervention (condition = 1) versus receiving the 4-month waitlist (condition = 0). Thus, these models compared pre-intervention and immediate post-intervention outcomes in the immediate intervention group with 4-months pre-intervention and pre-intervention outcomes in the waitlist control group. Effect sizes (d) for linear mixed models were calculated as mean pre-post change in the immediate intervention group minus the pre-post change in the waitlist control group, divided by the pooled baseline standard deviation (Morris, 2008).

To examine longer-term persistence of intervention efficacy, we secondarily limited analyses to the immediate intervention group and compared 8-months post-baseline assessment (time = 2; changed from 6-months post-baseline prior to the beginning of the study) to both baseline (time = 0) and 4-months post-baseline assessment (time = 1). Differences between

baseline and 4-month follow-up would indicate delayed efficacy if differences were detected at 4-month follow-up but not post-intervention. Differences between 4-months post-baseline assessment and 8-months post-baseline assessment would reveal whether efficacy was maintained, increased, or decreased from 4-months post-baseline assessment. Effect sizes (d) were calculated as mean change from baseline- and 4-months post-baseline to 6-months post-baseline divided by the baseline immediate intervention standard deviation accounting for correlation between time points (Morris & DeShon, 2002).

All results were evaluated at $p < .05$. We report means, standard errors, 95% confidence intervals, and effect sizes.

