For the simulated practice videos, two bachelors-level research assistants independently coded the 587 responses (baseline = 235; 4-months post-baseline = 189; 8-months post-baseline = 163). Two post-doctoral researchers trained the two coders in identifying LGBTQ-affirmative CBT principles and intervention strategies based on the content of the training. All responses were given unique identification codes so that coders were masked to the assessment time-point and condition of each response. Inter-rater reliability was assessed via intra-class correlation (ICC) estimates based on a two-way mixed effects model. A post-doctoral researcher calculated ICCs for the average total of LGBTQ-affirmative CBT skills items and the average total of general CBT skills items. The coders initially met with the post-doctoral researchers after every 20 coded responses. The post-doctoral researchers led coding meetings to establish consensus on any inconsistently applied ratings. In cases where the coders could not reach consensus, the post-doctoral researchers met with both coders to resolve the discrepancy. ICC estimates were deemed indicative of poor reliability for values less than .5, moderate reliability between .5 and .75, good reliability between .75 and .9, and excellent reliability greater than .9 (Koo & Li, 2016;

Portney & Watkins, 2000). Once excellent inter-rater agreement was reached, one of the research assistants coded the remaining responses in intervals of 100 responses, while the other research assistant coded 20 of those 100 responses to continue assessing inter-rater reliability. Overall, the average ICC for the LGBTQ-affirmative CBT skills items was .87 and the average ICC for the general CBT skills items was .81.

References

- Byrne, B. M. (2010). *Structural equation modeling with AMOS: Basic concepts, applications, and programming* (2nd ed.). Routledge/Taylor & Francis Group.
- Koo, T. K., & Li, M. Y. (2016). A guideline of selecting and reporting intraclass correlation coefficients for reliability research. *Journal of Chiropractic Medicine, 15*(2), 155-163.
<https://doi.org/10.1016/j.jcm.2016.02.012>
- Morris, S. B. (2008). Estimating effect sizes from pretest-posttest-control group designs. *Organizational Research Methods, 11*(2), 364-386.
<https://doi.org/10.1177/1094428106291059>

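### The primary Condition × Time test is in essence a change-score comparison: valid, but usually less precise than a baseline-adjusted analysis of the same data

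*SAP*

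**What the plan says.** The SAP (Intervention Efficacy) uses "linear mixed models with maximum likelihood estimation and an unstructured covariance matrix" and tests Condition × Time for eight outcomes. It restricts the data: "Primary analyses between conditions were limited to baseline (time = 0) and 4-months post-baseline assessment (time = 1". The effect size is the "mean pre-post change in the immediate intervention group minus the pre-post change in the waitlist control group", divided by the pooled baseline SD. Protocol 7.2 planned the same contrast at 3 months.

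On the analysis set, the SAP says: "Intervention efficacy was assessed using an intent-to-treat analysis and included all participants", with 61 immediate and 60 waitlist. Age, full-time employment and years in LGBTQ mental health care differed between arms at p < .10. "Thus, we included fulltime employment status and number of years working in LGBTQ mental health care as covariates in subsequent analyses". Age was left out because it correlated .50 with years. The SAP does not say whether the covariates enter as main effects only or also interact with time. Neither document adjusts for the baseline score, sets the arms' baseline means equal, or gives a baseline to 4-month correlation.

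**The concern.** Randomised arms share one expected baseline mean. A model that estimates a separate baseline mean for each arm and then tests the difference in change does not use that fact. The resulting noise in the baseline difference passes into the treatment estimate. The baseline scores are already in the data set, so using them as an adjuster would tighten the intervals at almost no cost. The loss matters most for outcomes with a weak baseline to 4-month correlation and for true effects below the planned d = 0.66.

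A second point depends on how the model was coded. A covariate that does not vary over time and enters only as a main effect shifts both visits equally, so it drops out of a change contrast. The efficacy test could then be described as adjusted for the imbalanced characteristics when the tested coefficient is not.

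**Working it through.** **The plan's own figure.** Protocol 7.1 uses a two-sample t-test with d = 0.66, two-sided alpha 0.05 and 80% power. The exact solution is 37.02, so 38 per group, with power 0.810 at 38. This reproduces the protocol. The calculation uses no pre-post correlation.

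**Inputs.**
- Randomised: 61 and 60 (SAP).
- Follow-up: the only 4-month count is of coded vignette responses, "baseline = 235; 4-months post-baseline = 189". 189/235 = 0.80, or about 48 per arm. This is a proxy for the questionnaire and quiz outcomes.
- Split by arm: Protocol 4.2.1 says "2 brief video clips (less than 1 minute each) of fictional clients will be presented", so 189/2 = 94.5, at least 95 participants. The SAP's acceptability counts are "immediate $n = 52$, waitlist control $n = 44". The 52 were taken at 4 months, but the 44 belong to the waitlist arm's later post-training assessment. That suggests 52 and 95 − 52 = 43, an assumed split used as a check.
- Not in the documents, so assumed over a range: rho (baseline to 4-month correlation) and k (4-month SD divided by baseline SD).

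**Equivalence.** With two visits, unstructured covariance, free baseline means and complete pairs, the Condition × Time coefficient equals the difference in mean change. Numerical fits with two main-effect covariates agreed to within 1e-15. With missing follow-up, the model also uses the baselines of those not followed, so the identity is close but not exact.

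**Variance, in baseline SD units** (N randomised and n followed per arm, loss at random, summed over arms):
- Condition × Time: k²(1 − rho²)/n + (k·rho − 1)²/N
- Baseline-adjusted: k²(1 − rho²)/n

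The difference is the second term, which is zero only when k·rho = 1, that is, when the slope is 1.

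Example, k = 1 and rho = 0.5: adjusted 0.75/48 + 0.75/48 = 0.0313. Extra term 0.25/61 + 0.25/60 = 0.0083. Condition × Time 0.0395. Ratio 0.79.

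Power is from the noncentral t at d = 0.66, with df = 94 (SAP) and 93 (adjusted), 48 followed per arm:

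| k | rho | Variance ratio | Variance saving | SE saving | Power, SAP | Power, adjusted |
|---|---|---|---|---|---|---|
| 1.0 | 0.3 | 0.70 | 30% | 16% | 0.802 | 0.918 |
| 1.0 | 0.5 | 0.79 | 21% | 11% | 0.908 | 0.959 |
| 1.0 | 0.7 | 0.88 | 12% | 6% | 0.987 | 0.994 |
| 1.3 | 0.3 | 0.84 | 16% | 8% | 0.657 | 0.732 |
| 1.3 | 0.5 | 0.93 | 7% | 4% | 0.782 | 0.811 |
| 1.3 | 0.7 | 0.99 | 1% | under 1% | 0.930 | 0.931 |
| 0.8 | 0.3 | 0.56 | 44% | 25% | 0.880 | 0.987 |
| 0.8 | 0.5 | 0.63 | 37% | 21% | 0.955 | 0.996 |
| 0.8 | 0.7 | 0.68 | 32% | 18% | 0.996 | above 0.999 |

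**Where the SAP test falls below 80% power at d = 0.66.** Rho under about 0.30 at k = 1, under about 0.52 at k = 1.3, and under about 0.10 at k = 0.8. With 52 and 43 followed, the k = 1 threshold is 0.31. At k = 1 and rho 0.3, the detectable effect at 80% power is 0.66 against 0.55. For an illustrative d = 0.40 at k = 1, power is 40% against 53% at rho 0.3 and 51% against 61% at rho 0.5.

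**Bias.** In simulation with a true effect of 0.66 and no covariate imbalance, both estimators averaged 0.657 to 0.663, with complete data and with 20% random loss.

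**Covariates** (assumed: one covariate differing by 0.33 SD between arms, level effect 0.3).
- Baseline adjustment that omits this covariate is off by about 0.33 × 0.3 × (1 − slope). The pooled slope is (rho + 0.09)/1.09, where rho is the residual correlation: 0.36, 0.54 and 0.72 at rho 0.3, 0.5 and 0.7. The error is therefore about 0.06, 0.05 and 0.03, giving 0.56, 0.55 and 0.53 for a true 0.50.
- If the covariate also predicts change by 0.2 per SD, a main-effect term leaves 0.33 × 0.2 = 0.066. In simulation at residual rho 0.5 the estimate was 0.565, against 0.498 with a covariate × Time term.

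**The case against.** The plan contains no error on this point. Protocol 7.2 specified the contrast and its effect size in advance, the SAP follows both, and hypothesis 2 in Protocol 3.2 asks about greater improvement. The choice is between two legitimate estimators, the SAP already reports results, and a post hoc analysis cannot change the primary inference. All of that stands. It limits the point to a suggested sensitivity analysis. It does not remove the precision difference, because under randomisation both methods estimate the same mean difference.

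The gain also rests on unstated inputs and can almost vanish. A reader might infer that appreciable precision is lost on every outcome. The documents do not support that: at k = 1.3 and rho 0.7 the variance saving is about 1%. Nor can d = 0.66 be carried directly to general CBT simulated practice, which is analysed on a square-root scale.

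The strongest statistical objection is robustness. Change scores resist a stable baseline imbalance without help, whereas baseline adjustment relies on the covariates, and the SAP reports three imbalanced characteristics. This stands too. It is why age belongs in the added model: r = .50 with years is only 25% shared variance, too little to make age redundant.

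**Conclusion.** The concern holds as a matter of efficiency. The primary test is in essence a change-score comparison, valid under randomisation and missing at random, and less precise than a baseline-adjusted analysis unless the slope of the 4-month score on baseline is 1. The size depends on assumed rho and SD ratio and on the 80% follow-up proxy: about 12% to 30% of the variance with equal SDs over rho 0.3 to 0.7, 1% to 16% at SD ratio 1.3, and 32% to 44% at 0.8.

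Two stronger readings are tempting. One is that the test is biased or badly underpowered. Nothing in the documents shows bias, and with equal SDs power for d = 0.66 stays at 80% or more once rho reaches about 0.30. The other is that the covariates certainly do no work. The SAP does not say how they enter, so this is conditional: if they are main effects only, they cancel from the tested coefficient with complete pairs and barely move it otherwise (0.007 to 0.016 SD on average in simulation).

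**What to change.** For each of the eight outcomes, report a baseline-adjusted estimate with its 95% CI beside the existing result, in one of two forms:

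- Regress the 4-month score on condition, baseline score, full-time status, years in LGBTQ care and age.
- Fit the mixed model with a common baseline mean, unstructured covariance, and main effects and covariate × Time terms for the same three covariates. This form also keeps participants without a 4-month score.

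Do not adjust for baseline while leaving the imbalanced covariates out.

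Label the addition a post hoc sensitivity analysis and leave the SAP model primary. Divide by the pooled baseline SD to keep the effect-size scale (on the square-root scale for general CBT simulated practice). State how full-time status and years enter the primary model. If they are main effects only, do not describe that test as covariate-adjusted. Record the omission of age as a departure from Protocol 7.2, which retains any differing characteristic.

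The cost is a few lines of model code, a few degrees of freedom and eight extra labelled estimates, with no new data. The trade-off is reliance on the covariates to handle baseline imbalance.

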7.1 Sample Size Considerations

Our team's prior pilot studies assessing the efficacy of LGBTQ-affirmative health trainings have demonstrated moderate-to-large effect sizes in improving healthcare providers' LGBTQ-affirmative clinical skills and willingness to provide LGBTQ-affirmative clinical care ($d = 0.66-1.20$) (Lelutiu-Weinberger & [name], 2017, Lelutiu-Weinberger, [name] & [name], in preparation; White Hughto, [name], et al., 2017). Based on the most conservative effect size drawn from our team's previous LGBTQ-affirmative training studies for healthcare providers ($d = 0.66$), we conducted a power analysis for an independent samples t -test used to compare the mean of a continuous measurement in two samples. We set the threshold probability for rejecting the null hypothesis (type I error rate) to α (two-tailed) = 0.05. Power to detect Type I error was fixed at a standard level of $1 - \beta = 0.80$ (type II error rate). Given these parameters, we require 38 participants per group ($N = 76$) to retain statistical power. We expect to enroll at minimum 38 participants per group; due the high need and reach of our recruitment partner (i.e., CenterLink, the coordinating hub of the United States 250+ LGBTQ community centers), we expect to enroll at least 100 participants which will allow for adequate statistical power even with 20% attrition.

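### The SAP's persistence rule calls efficacy delayed by setting one significant result against one non-significant result, and does not use the 8-minus-4-month contrast it already plans

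*SAP*

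**What the plan says.** The last part of the SAP's Intervention Efficacy section is limited to the immediate-training arm. It compares 8 months post-baseline "to both baseline (time = 0) and 4-months post-baseline assessment (time = 1"), so it lists two within-arm contrasts: 8 months versus baseline, and 8 versus 4 months.

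Each contrast is given a meaning. For the first, differences between "baseline and 4-month follow-up would indicate delayed efficacy if differences were detected at 4-month follow-up but not post-intervention". Here the 4-month follow-up has to mean 4 months after training, that is, 8 months post-baseline, because 4 months post-baseline is itself the post-intervention visit. For the second, the 4- to 8-month "assessment would reveal whether efficacy was maintained, increased, or decreased from 4-months post-baseline assessment". The section closes: "All results were evaluated at $p < .05$. We report means, standard errors, 95% confidence intervals, and effect sizes".

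The only post-intervention test described in the section is the between-arm Condition × Time test of the primary analysis. A within-arm 4-month versus baseline contrast is not listed. Protocol 7.2 planned only the post-training to follow-up comparison in the immediate arm and has no rule for delayed efficacy.

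**The concern.** One result below .05 and another above it can differ by chance alone. A claim that an effect arrived late is a claim about the change between 4 and 8 months, and only the 8-minus-4-month contrast tests that. As written, an outcome with the same true gain at both visits can be called delayed because the 4-month test happened to miss. The same outcome can then show no detectable 4- to 8-month change under the SAP's next sentence, so that the two interpretations conflict.

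The undefined post-intervention verdict makes this worse. If it is the Condition × Time test, a comparison across two arms is set against a more precise one within a single arm, and the two verdicts will disagree more often.

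What is at stake is the reported timing of the training effect on eight outcomes, in a secondary analysis with no control group.

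**Working it through.** **The plan's own figure.** Protocol 7.1 takes its effect from "previous LGBTQ-affirmative training studies for healthcare providers ($d = 0.66") with two-sided α = 0.05 and power 0.80. The exact two-sample t calculation gives 37.02, rounded up to 38 per group, with power 0.81 at 38. The protocol's figure reproduces. It does not bear on the delayed rule beyond supplying the 0.66 SD benchmark.

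**Sample sizes (inferred).**
- The acceptability measure was "presented to participants immediately following the intervention (immediate $n = 52$, waitlist control $n = 44"). I take 52 as the immediate arm at 4 months.
- The SAP counts 189 coded video responses at 4 months and 163 at 8 months, with two videos per person: 189/2 ≈ 95 and 163/2 ≈ 82 people. Odd counts show that some people gave one response, so these are lower bounds.
- Waitlist at 4 months: 95 − 52 = 43.
- Immediate arm at 8 months: 82 − 44 = 38; 82 × 61/121 ≈ 41; 82 × 52/95 ≈ 44 or 45. I use 38 to 44.

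**Other assumptions, not in the documents.** SD 1, equal correlation ρ of 0.5 or 0.7 between visits, 8-month responders nested in 4-month responders, and no waitlist change unless stated.

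**Formulas.** Within-arm change: SE = √[2(1−ρ)/n]. Between-arm difference in change: SE = √[2(1−ρ)(1/52 + 1/43)].

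**Hand check at a constant 0.66 SD gain.**
- Within-arm, ρ = 0.5: SE = √(1/52) = 0.139 and z = 0.66/0.139 = 4.8. The 4-month test almost never misses.
- Between-arm, ρ = 0.5: SE = √(0.0192 + 0.0233) = 0.206 and z = 3.20. Probability of a miss ≈ Φ(1.99 − 3.20) = 0.11.
- Between-arm, ρ = 0.7: SE = √(0.6 × 0.0425) = 0.160 and z = 4.13. Probability of a miss ≈ Φ(1.99 − 4.13) = 0.02.
- If the waitlist rises 0.2 SD, the difference is 0.46 SD, so z = 2.23 (ρ = 0.5) or 2.88 (ρ = 0.7), with misses of about 0.40 and 0.19.

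**Simulation** (paired t within arm, two-sample t on change between arms). Probability of a positive delayed label when the true values at 4 and 8 months are equal:

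| Constant true gain | Within-arm | Between-arm |
|---|---|---|
| 0 | about 2% | about 2% |
| 0.2–0.4 SD | 3–15% | 17–35% |
| 0.66 SD | at most 0.3% | 2–11% |
| 0.66 SD, waitlist rises 0.2 SD | at most 0.3% | 19–39% |
| 1.2 SD | about 0 | about 0 |

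A lower correlation raises the rates: with ρ = 0.3 and 0.66 SD they are about 2% and 21–22%. A check with a maximum-likelihood, unstructured-covariance model on the within-arm reading gave 2.8–15.4% at 0.2–0.4 SD and at most 0.2% at 0.66 SD.

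**Adding the direct contrast.** With no true 4- to 8-month change, a 95% CI for that change lies wholly above 0 with probability 2.5%, so the combined rule cannot exceed that, whatever the gain or the waitlist does. Simulated values were 0.5–1.9% (within-arm) and 1.4–2.1% (between-arm) at 0.2–0.4 SD, and at most 0.1% and 0.8% at 0.66 SD. The likelihood-model check gave at most 2.4%.

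**Precision of that contrast.** CI half-width = t × √[2(1−ρ)/n]. For ρ = 0.5 and n = 38: 2.026 × √(1/38) = 0.33 SD. For ρ = 0.7 and n = 44: 2.017 × √(0.6/44) = 0.24 SD. A non-significant 4- to 8-month change is therefore compatible with a loss of roughly a quarter to a third of an SD.

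**The case against.** The best defence is that the SAP largely supplies its own correction. The 8-versus-4-month comparison is planned, CIs and effect sizes are promised for all results, and the wording is interpretive, not a formal decision rule. A false delayed label would sit beside a direct contrast showing no detected rise. That stands, and it limits the severity. It does not rescue the rule, because nothing makes the direct contrast a condition for the label.

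The second point is size. The protocol's prior effects are described for skills and "willingness to provide LGBTQ-affirmative clinical care ($d = 0.66-1.20"). Within that range the within-arm error is negligible. The larger rates need a smaller gain, the between-arm reading, or both. This also stands. Some of the eight outcomes may have smaller effects, but the documents do not say so.

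A reader might infer several stronger things that the documents do not support:
- That the SAP equates a non-significant 4- to 8-month change with maintained efficacy. It does not say so; it merely gives no other criterion.
- That an outcome was in fact mislabelled. The SAP is dated 12.7.21 and written in the past tense, but it reports no outcome meeting the condition.
- That the error touches only the timing of a real gain. With no true change, a positive label still appears about 2% of the time.
- That the between-arm rates are firm. They depend on the assumed waitlist change.

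Finally, the repaired rule still separates a delayed gain from an increasing one by a non-significant 4-month result. That is a fair limit. The rise itself is tested, but the word delayed remains descriptive.

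**Conclusion.** The rule is wrong as written, with low-to-moderate severity. It infers a change over time from two verdicts, omits the contrast that would test it, and leaves the post-intervention verdict undefined. The primary Condition × Time analysis is unaffected.

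The practical error ranges from negligible, for gains at or above the planning effect on the within-arm reading, to about one trial in three per outcome, for gains of 0.2–0.4 SD on the between-arm reading. These rates rest on assumed correlations, inferred sample sizes and an assumed waitlist course. The logical fault does not depend on them.

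Using the direct contrast repairs the inference about timing only. The comparison stays uncontrolled, because the waitlist arm has been trained by 8 months.

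**What to change.** 1. Call efficacy delayed only if, in addition to the existing condition, the 8-minus-4-month 95% CI lies above 0.
2. State that post-intervention in this rule means the within-arm 4-month versus baseline contrast, and report that contrast.
3. If the existing condition is met but the CI includes 0, report a gain at 8 months with its timing not resolved.
4. Report the 8-minus-4-month estimate and CI for every outcome, and do not infer maintained efficacy from a non-significant change alone.
5. Describe the section as an uncontrolled, within-arm comparison.
6. Editorial: the effect-size sentence refers to "mean change from baseline- and 4-months post-baseline to 6-months post-baseline divided by the baseline immediate intervention standard deviation"; its 6-month visit should agree with the 8-month visit named in the same paragraph. Say also that the 4-month follow-up means 4 months after training.

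**Cost.** Wording, and one further contrast from visits already collected. Given the SAP's date, this is a correction to interpretation and reporting. The price is sensitivity to true delay: for a rise from 0 at 4 months to 0.4 SD at 8 months, the label is earned in about 51–85% of trials instead of 65–89%. For a rise from 0 to 0.66 SD the figure is almost unchanged (94–97% against 95–97%).
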